## 12.2.2 Criterion for Increased Liver Chemistry Monitoring While Continuing Study Drug

Criterion for Increased Liver Chemistry Monitoring and Follow-up Actions	
Criterion	Actions
$ALT \geq 3x$ ULN and $<5x$ ULN and bilirubin $<2x$ ULN, without symptoms believed to be related to liver injury or hypersensitivity, and can be monitored weekly for 4 weeks	

Notify the Medical Monitor within 24 hours of learning of the abnormality to discuss subject safety.

Subject can continue study drug.

Subject must return weekly for repeat liver chemistry tests (ALT, AST, alkaline phosphatase, bilirubin) until the abnormalities resolve, stabilize, or return to baseline.

If at any time the subject meets liver chemistry stopping criteria, proceed as described in Section 7.2.1 and Section 12.2.1.

	

• If, after 4 weeks of monitoring, ALT <3x ULN and bilirubin <2x ULN, monitor per standard scheduling for remainder of study and follow-up period.

--	--

### **12.2.3 Restart Following Transient Resolving Liver Chemistry Events Not Related to Study Drug**

The Investigator may request the Sponsor to consider restarting study drug in a subject who stopped study drug because of a liver chemistry event. Approval for study drug restart can be considered under the following circumstances:

- Liver chemistry events have a clear underlying cause (e.g., biliary obstruction, pancreatic events, hypotension, acute viral hepatitis), liver chemistry tests have improved to normal or are within 1.5x baseline, and ALT <3x ULN.
- Possible drug-induced liver injury (DILI) has been excluded by the Investigator and the study team. This includes the absence of markers of hypersensitivity (otherwise unexplained fever, rash, eosinophilia). Where a study medication has an identified genetic marker associated with liver injury (e.g., lapatinib, abacavir, amoxicillin/clavulanate), the presence of the marker should be excluded. If study drug-related liver injury cannot be excluded, the guidance on appropriate action and follow-up in the previous sections of this Appendix will apply.
- There is no evidence of alcoholic hepatitis.
- Medical Monitor approval of study drug restart has been obtained.

#### **If restart of study drug is approved by the Sponsor in writing:**

- Study drug must be administered at the dose specified by the Sponsor.
- Subjects approved by the Sponsor for restart of study drug must return to the clinic twice a week for liver chemistry tests until stable liver chemistry tests have been demonstrated, and then standard laboratory monitoring may resume as per protocol.
- If the subject meets protocol-defined liver chemistry stopping criteria after study drug restart, study drug should be permanently discontinued.
- The Medical Monitor must be informed of the outcome for the subject following study drug restart.
- The Sponsor must be notified of any AEs.

## 12.3 Appendix of Potentially Clinically Significant Adverse Events

### 12.3.1 List of Potentially Clinically Significant Signs and Symptoms

Event	Description
Abdominal Pain	Pain and abdominal tenderness to palpation that significantly impairs ambulation, food intake, and ADL for >24 hours
Nausea/Vomiting	>3 episodes of emesis over >4 continuous hours with continuous nausea
Diarrhea	>3 episodes of unformed stools and fecal urgency over >8 hours
Dizziness/Hypotension	Orthostatic CNS symptoms (dizziness, confusion) that prevent ambulation for >3 hours, associated with orthostatic SBP decrease >20 mmHg or DBP decrease >10 mmHg or upright heart rate >105 bpm, and are not vasovagal responses to provocative stimuli (e.g., phlebotomy, nausea, bowel or bladder function)
Sensorium	Disorientation to time, place, or identity. Any abnormal ideation.
Mood	Feelings of grief or loss that interfere with study procedures. Any suicidal ideation.
Headache/Pain	Any focal or generalized head pain that disrupts normal activities over >12 hours and is not responsive to 2 doses of non-steroidal analgesics
Pruritis	Generalized itching over >24 hours unresponsive to oral antihistamine
Systolic Blood Pressure	>30 mmHg increase from baseline values or an absolute level >180 mmHg
Diastolic Blood Pressure	>20 mmHg increase from baseline values or an absolute level >110 mmHg
Heart Rate	Resting (sitting or recumbent) HR >110 bpm
Cardiac Rhythm	Any rhythm other than sinus rhythm, sinus bradycardia, or mild sinus tachycardia
QRS Morphology	Significant prolongation of QRS interval or new onset of bundle branch block
Skin Rash	Pruritic rash or urticaria over >100 cm  in area in more than one location simultaneously
Neurological Signs	New onset of readily visible tremor during normal movement, clonic reflexes, or motor dyscoordination, convulsions, or seizures

Abbreviations: ADL, activities of daily living; bpm, beats per minute; CNS, central nervous system; DBP, diastolic blood pressure; HR, heart rate; SBP, systolic blood pressure.

### 12.3.2 List of Potentially Clinically Significant Laboratory Findings

Lab	Criteria
Hemoglobin	>2 g/dL reduction from baseline or absolute value <10 g/dL
Neutropenia	Absolute neutrophil count <1,800/ $\mu$ L and >500/ $\mu$ L reduction from baseline
Lymphopenia	Absolute lymphocyte count <500/ $\mu$ L
Platelet count	<50,000/ $\mu$ L

Lab	Criteria
Creatinine	>1.8 mg/dL or >0.4 mg/dL increase from baseline value
BUN	>30 mg/dL and >10 mg/dL increase from baseline values
ALT	>3-fold above laboratory reference upper limit value
AST	>3-fold above laboratory reference upper limit value
Bilirubin (total)	>1.5-fold above laboratory reference upper limit value
Potassium	<3.0 or >5.5 meq/L
Sodium	<130 or >150 meq/L
Serum calcium	>11.4 mg/dL sustained over 24 hours
FSH	>15 if baseline value was <5

Abbreviations: ALT, alanine aminotransferase; AST, aspartate aminotransferase; BUN, blood urea nitrogen; FSH, follicle-stimulating hormone.

Note: If a laboratory result meets any of these criteria, it should be confirmed by repeat measurement within 48 hours.

## 12.4 Appendix of Clinical Laboratory Tests

Laboratory Assessments	Parameters	
Hematology	Platelet count	
	RBC count	
	RBC indices: MCV, MCH, % reticulocytes	
	Hemoglobin	
	Hematocrit	
WBC count		
	Differential: neutrophils, lymphocytes, monocytes, eosinophils, basophils	
Clinical Chemistry 	Glucose, fasting	Alkaline phosphatase
	Potassium	ALT/SGPT
	Calcium	AST/SGOT
	Sodium	GGT
	BUN	Total and direct bilirubin
	Creatinine	Total protein
Lipid Panel	Total cholesterol, LDL, HDL, triglycerides	
Thyroid Panel	T3, T4, TSH	
Routine Urinalysis	Specific gravity pH, glucose, protein, blood, ketones, bilirubin, urobilinogen, nitrite, by dipstick Microscopic examination (if blood or protein is abnormal)	
Other Tests	LH, FSH, inhibin B, SHBG, renin, aldosterone For females only: estradiol, prolactin, progesterone	

Abbreviations: ALT = alanine aminotransferase; AST = aspartate aminotransferase; BUN = blood urea nitrogen; FSH = follicle-stimulating hormone; GGT = gamma-glutamyltransferase; HDL = high-density lipoprotein; INR = international normalized ratio; LDL = low-density lipoprotein; LH = luteinizing hormone; MCH = mean corpuscular hemoglobin; MCV = mean corpuscular volume; RBC = red blood cell; SAE = serious adverse event; SGOT = serum glutamic-oxaloacetic transaminase; SGPT = serum glutamic-pyruvic transaminase; SHBG = sex hormone-binding globulin; TSH = thyroid-stimulating hormone; ULN = upper limit of normal; WBC = white blood cell.

 Details of liver chemistry stopping criteria and required actions and follow-up assessments after liver stopping or monitoring event are given in [Section 12.2](#). All events of ALT  $\geq 3 \times$  ULN plus bilirubin  $\geq 2 \times$  ULN ( $>35\%$  direct bilirubin) or ALT  $\geq 3 \times$  ULN plus INR  $> 1.5$  (if INR is measured) may indicate severe liver injury (possible Hy's Law) and must be reported as an SAE.

1. LIST OF ABBREVIATIONS

Table 1: List of Abbreviations

Abbreviation	Term
17-OHP	17-hydroxyprogesterone
A4	Androstenedione
ACTH	Adrenocorticotropin hormone, corticotropin
AE	Adverse Event
C	Continuous reporting format
CAH	Congenital adrenal hyperplasia
CRF	Case Report Form
CSR	Clinical Study Report
dy	Days
F	Frequency reporting format
G	Geometric mean reporting format
GCP	Good Clinical Practices
HbA1c	hemoglobin A1c
IRB	Institutional Review Board
ITT	Intent-to-Treat Population
LLN	Lower Limit of Normal
LOCF	Last Observation Carried Forward
MedDRA	Medical Dictionary for Regulatory Activities Terminology
MF	Multiple frequency reporting format
mitT	Modified Intent-to-Treat
mo	Months
N	Total Sample Size
OTC	Over the Counter Medication
PP	Per-Protocol Population
SD	Standard Deviation
SAE	Serious Adverse Event
SAP	Statistical Analysis Plan
SAS	Statistical Analysis System
SF-36	Short Form 36
TART	Testicular adrenal rest tumor
ULN	Upper Limit of Normal
WHO	World Health Organization
yr	Years

2. INTRODUCTION

This document outlines the initial plan for the summarization and analysis of clinical data collected in Study SPR001-202 for tildacerfont, SPR001.

The analysis of pharmacokinetics (data derivation and summary of individual PK parameters) is outside the scope of this document and is not addressed here.

This document describes the a priori plan for analysis. Once the analysis is in progress, it may become apparent from the data that the planned analysis should be modified. Any substantive modification to the original analysis plan will be identified in the clinical study report (CSR).

3. STUDY OBJECTIVES AND ENDPOINTS

3.1. Study Objectives

3.1.1. Primary Objective

The primary objective is:

- To evaluate the safety of SPR001 in subjects with CAH.

3.1.2. Secondary Objectives

The secondary objectives are:

- To evaluate the efficacy of SPR001 in subjects with CAH in terms of changes in hormones.

3.1.3. Exploratory Objectives

The exploratory objectives are:

- To evaluate the effect of SPR001 on quality of life (QoL), metabolic parameters, exploratory adrenal hormones, and sex-specific outcomes in subjects with CAH.

3.2. Study Endpoints

3.2.1. Safety Endpoints

The safety endpoints of this study include the following:

- Adverse events (AE) and Serious adverse events (SAE).

Additional safety endpoints include the following:

- Change from baseline in safety laboratory, vital signs, and electrocardiogram (ECG) parameters,
- Clinical changes as determined by physical examinations (including testicular ultrasound for males),
- Suicidality as measured by the Columbia-Suicide Severity Rating Scale (C-SSRS), and
- Hospital Anxiety and Depression Scale (HADS)
- Concomitant medication usage.

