### 3 OBJECTIVES AND ENDPOINTS

Objectives	Endpoints
Primary	
• To evaluate the safety of SPR001 in subjects with CAH	

• AEs, SAEs, AEs leading to discontinuation/withdrawal, DLTs, and AESIs

• Physical examination findings

• Vital signs

• Changes in ECG

• Changes in clinical laboratory values

• Changes in the C-SSRS and the HADS

Secondary	
• To evaluate the efficacy of SPR001 in subjects with CAH in terms of changes in hormones	

• Changes in ACTH, 17-OHP, androstenedione, and testosterone

Exploratory	
• To evaluate the effect of SPR001 on QoL, metabolic parameters, exploratory adrenal hormones, and sex-specific outcomes in subjects with CAH	

• Changes in QoL as measured using the SF-36, PGIC, bother score, and CAH signs and symptoms interview

• Changes in fasting glucose, HbA1c, fasting insulin, and lipid profile

• Changes in BW and BMI

• Changes in exploratory adrenal hormones

• Changes in TARTs and on semen analysis in male subjects

• Changes in acne, hirsutism, and menstrual cyclicity in female subjects

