## 7 DOSE REDUCTION, STUDY DRUG DISCONTINUATION, AND PARTICIPANT WITHDRAWAL

### 7.1 Dose-Limiting Toxicity and Dose Reduction

A DLT is defined as a Grade 3 or higher TEAE considered at least possibly related to study drug. If a subject experiences a DLT, the Investigator may reduce the subject's daily dose of SPR001 (by 50 to 200 mg), depending on the TEAE, in order to keep the subject on study. A Grade 3 or higher TEAE considered related to study drug will also be considered an AESI (see [Section 8.2.8](#)). Potential dose reductions must be discussed with the Medical Monitor. At any time during the study, subjects who experience any clinically significant signs of acute adrenal insufficiency (e.g., postural hypotension, nausea, abdominal pain) may have their study drug dose reduced or withheld and/or their glucocorticoid replacement therapy modified (see [Section 7.2.4](#)).

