### **8.2.8 Adverse Events of Special Interest**

AESIs are those AEs that do not meet SAE criteria but must be monitored on an ongoing basis. These events will be reported on the SAE Report Form, allowing for the collection of additional information, as warranted. The following will be considered AESIs for this study:

- Suicidality as indicated by type 3, 4, or 5 ideation on the C-SSRS (see [Section 7.2.3](#) regarding study drug stopping criteria and [Section 8.1.6.1](#) regarding the C-SSRS). This should be reported as an AESI until it becomes serious according to the SAE definition (e.g. hospitalization).
- High HADS score or other indication of worsening depression (see [Section 7.2.5](#) regarding study drug discontinuation and [Section 8.1.6.2](#) regarding the HADS)
- Significant liver chemistry changes that do not satisfy stopping rules (see [Section 7.2.1](#) and [Section 12.2.1](#)). Cases of Hy's Law should be reported as SAEs.
- Severity Grade 3 or higher TEAE considered related to study drug (see [Section 7.1](#) regarding dose reduction)

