### **9.3.5 Safety Analyses**

Safety analyses will be performed on the Safety Population.

AEs will be coded using MedDRA Version 20 or higher and presented by System Organ Class and Preferred Term. AEs that occur before the first dose of study drug will be distinguished from TEAEs. TEAEs will be listed by subject and summarized overall and by SPR001 dose, if applicable. The incidence of each TEAE will be tabulated and presented by maximum severity. The frequency (number and percentage) of subjects who experience  $\geq 1$  TEAE will be summarized. TEAEs potentially related to study drug, SAEs, AEs leading to study drug discontinuation/study withdrawal, DLTs, and AESIs will be summarized by frequency of subjects who experience  $\geq 1$  event and/or tabulated by incidence for each event.

Physical examination findings will be listed. Vital signs, ECG parameters, and clinical laboratory values will be listed and summarized using descriptive statistics. Investigators' assessments of ECG results will be listed and summarized in a frequency table. Clinical laboratory values may be presented in shift tables. Prior and concomitant medications will be listed. C-SSRS data will be listed. Data for the HADS (including anxiety and depression subscales) will be summarized using descriptive statistics.

An SRC will review safety data at regular intervals throughout the study (see [Section 10.6](#)).

Additional analyses may be performed if warranted upon review of the data.

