8.1. Adverse Event Preferred Term and Body/Organ System Summary Tables

Adverse events will be coded to the preferred terms of the Medical Dictionary for Regulatory Activities (MedDRA®). Summaries will present by system organ class (SOC), preferred term (PT) and severity and/or relatedness, the frequency and percentage of subjects reporting each observed event.

A treatment-emergent adverse event (TEAE) will be defined as any AE that begins on or after the date of first dose of study drug up to the date of last dose of study drug plus the number of days in the follow-up period. AEs observed during the period from obtaining informed consent to the start of administration of study drug will be regarded separately from TEAEs.

All AEs and all TEAEs will be listed by subject.

Subjects who experienced treatment-limiting AEs will be listed. Treatment-limiting AEs are defined as any event that leads to permanent or temporary discontinuation from treatment, or a reduction in the treatment dose.

Summary of adverse events will be dependent on adverse events observed. If no adverse events meeting a specific table are observed, the summary table will not be completed. Blank summary tables will not be utilized.

The following is the list of adverse event tables:

Overall:

- Overall Summary of Adverse Events

Label	Reporting Format
Adverse Event	F
Moderate or Severe Adverse Event	F
Adverse Event Related to Study Drug	F
Moderate or Severe Adverse Event Related to Study Drug	F
Serious Adverse Event	F
Serious Adverse Event Related to Study Drug	F
Adverse Events Leading to Permanent Study Drug Discontinuation	F
Adverse Events Leading to Temporary Interruption of Study Drug	F
Death During Study	F

By preferred term:

- Treatment-emergent Adverse Events by PT
- Treatment-emergent Adverse Events by SOC and PT

By severity:

- Treatment-emergent Adverse Events by SOC, PT and Severity
- Serious Adverse Events
- Deaths during Study

By relatedness:

- Drug-Related Treatment-emergent Adverse Events by SOC and PT
- Drug-Related Treatment-emergent Adverse Events by SOC, PT and Severity
- Drug-related Serious Adverse Events

Other:

- Adverse events leading to premature study drug discontinuation

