8.7. Hospital Anxiety and Depression Scale

Hospital Anxiety and Depression Scale is a 14-question scale. Seven questions compose the anxiety domain with scores of 0 to 3 with 3 representing a maximum response and 0 representing a minimal response. Seven questions compose the depression domain with scores of 0 to 3 with 3 representing a minimal response and 0 representing a maximal response.

The summary will summarize the anxiety, depression and total scores at each time point using a continuous reporting format.

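### The SAP plans no count of subjects with a dose-limiting toxicity or an adverse event of special interest, although the protocol makes both primary safety endpoints, and it does not declare the difference

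*SAP*

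**What the plan says.** **Protocol.** Section 3 (and the same list in the synopsis) gives the adverse-event part of the primary endpoint as "AEs, SAEs, AEs leading to discontinuation/withdrawal, DLTs, and AESIs". Section 9.3.5 commits to reporting them: "DLTs, and AESIs will be summarized by frequency of subjects who experience" one or more events, and/or tabulated by incidence. Both terms are defined. In 7.1, "A DLT is defined as a Grade 3 or higher TEAE considered at least possibly related to study drug". Section 8.2.8 lists four kinds of AESI: C-SSRS ideation of type 3, 4 or 5; a high HADS score or other sign of worsening depression; "Significant liver chemistry changes that do not satisfy stopping rules"; and a related TEAE of Grade 3 or higher.

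**SAP.** Section 3.2.1 names "Adverse events (AE) and Serious adverse events (SAE") and then laboratory values, vital signs, ECG, physical examination, C-SSRS, HADS and concomitant medication. The overall adverse event summary in 8.1 has nine rows; none is for DLTs or AESIs. The nearest row is "Moderate or Severe Adverse Event Related to Study Drug". For the HADS, section 8.7 says: "The summary will summarize the anxiety, depression and total scores at each time point using a continuous reporting format". Section 5.1.1 declares three changes from the protocol (acne and hirsutism, semen analysis, menstrual cyclicity) and no others. The final sample size in 4.3 is 11.

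**The concern.** Safety is the primary objective, and DLTs and AESIs are two of the named ways of measuring it. A programmer who follows the SAP exactly will produce no figure for either, and a reader of 5.1.1 will not learn that something the protocol promised is absent.

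The counts have a use. Protocol 2.2.4 and 4.3 support the starting dose by stating that Cohort A of Study SPR001-201 had no DLTs and no AESIs through 600 mg QD and 4 weeks of dosing. The natural question for a 12-week study is whether that still holds, and it needs the same two counts. Liver findings matter most here: protocol 2.3.1 reports ALT elevations in two Cohort A subjects at the highest dose tested, and liver chemistry change is one of the AESI categories.

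**Working it through.** No figure in the plan needs reproducing; this is a comparison of documents.

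**1. Primary endpoint list against SAP outputs**

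| Protocol endpoint | In SAP 3.2.1 | Row in SAP 8.1 overall summary | Own table in SAP 11.3 |
|---|---|---|---|
| AEs | yes | yes | 14.3.3.1.1 to 14.3.3.2 |
| SAEs | yes | yes | 14.3.3.4.1 |
| AEs leading to discontinuation | no | yes | 14.3.3.6.1 |
| DLTs | no | no | none |
| AESIs | no | no | none |

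The third line shows that absence from 3.2.1 does not by itself prove absence from the analysis. For DLTs and AESIs, 8.1 and 11.3 are also empty. Result: 5 − 3 = 2 endpoints without an output.

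**2. Can the DLT count be recovered from planned outputs?**

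- The moderate-or-severe related row pools Grade 2 with Grade 3 and above (taking the SAP's words as the protocol's Table 1 grades, with severe covering Grade 3 and higher). If that row shows x subjects, the number with a DLT could be anything from 0 to x.
- The treatment-limiting AEs in 8.1 are defined by what was done with study drug (stopped, interrupted or reduced). A DLT is defined by grade and relatedness. Neither set contains the other.
- Table 14.3.3.3.2 (related TEAEs by class, term and severity) is the closest. Protocol 8.2.3.2 counts possible, probable and definite as related, so its severe related events are essentially the DLTs. Two gaps remain. The SAP does not specify a line for subjects with at least one such event across terms. And 6.7.2 treats an AE with no grade as severe, so an ungraded related event would look like a DLT.

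**3. Can the AESI count be recovered?**

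| AESI category | Planned SAP output | What it gives | What it does not give |
|---|---|---|---|
| C-SSRS type 3 to 5 | 8.8; Table 14.3.8.2 | counts of positive ideation answers | a combined count for types 3 to 5 |
| High HADS or worsening depression | 8.7; Table 14.3.8.1; Listing 16.2.6.3 | minimum and maximum by visit; subject values | number of subjects with a subscale score above 12 (the level in protocol 7.2.5), or with other worsening |
| Liver chemistry | 8.4; Table 14.3.4.1.2.2; Listing 16.2.8.2.1 | shifts against the normal range; abnormal values | number of subjects with a liver AESI |
| Grade 3+ related TEAE | Table 14.3.3.3.2 | as in step 2 | as in step 2 |

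A shift table against the normal range puts every value above the upper limit in one category, so it cannot separate a slight elevation from a significant one. SAE tables cannot fill the gap, because 8.2.8 describes AESIs as events that do not meet the SAE criteria. No output combines the four categories.

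**4. What an explicit count would convey with n = 11** (assuming all 11 were dosed and so form the Safety Population)

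- One subject: 1/11 = 9.1%.
- No subjects: exact one-sided 95% upper bound 1 − 0.05^(1/11) = 23.8%; upper end of the exact two-sided 95% interval 1 − 0.025^(1/11) = 28.5%.

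These figures describe the study's precision, not an effect of the omission. They show why a stated 0/11 is information: it is compatible with a true rate above one in five. SAP 8.1 drops any adverse event table that would be empty, so without a count row a reader cannot tell none occurred from not tabulated.

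**The case against.** The strongest reply is that the content is planned and only the labels are missing. Much of this stands.

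- Protocol 9.3.5 permits tabulation by incidence instead of subject frequency, and Table 14.3.3.3.2 arguably delivers that for DLTs.
- A reader might infer that a subject crossing the HADS threshold would be invisible behind a flat mean. The documents do not support this. The continuous format in SAP 11.1 includes the minimum and maximum, and Listing 16.2.6.3 gives individual scores. SAP 8.7 scores the depression items in the opposite direction from protocol 8.1.6.2, but both extremes are shown: with seven items scored 0 to 3 the maximum is 21, so a score above 12 one way is a score below 9 the other way. What is missing is a count, and the scoring direction must be reconciled before one is derived.
- A reader might also infer that the endpoints were deliberately removed. That cannot be shown: the text of SAP 5.1.2, on revisions, was not available to this review. Omitted without declaration is as far as the evidence goes.
- DLTs and the Grade 3+ related AESI category largely coincide, so the two missing endpoints are not two independent losses.
- The 11.3 index may be updated after the SAP is final. That permits the outputs to be added but does not commit anyone to add them.

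What the reply does not answer is that no planned output gives the number of subjects with at least one DLT or at least one AESI, that high-HADS and liver AESIs have no count, and that 5.1.1 is silent.

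**Conclusion.** The point holds as a gap in planned primary reporting and in the declaration of changes. Two of the five adverse-event-type primary endpoints have no SAP summary. A reader might go further and conclude that part of the primary result will not be reported at all. That is too strong: the component events appear in the TEAE tables, the severity table, the C-SSRS and HADS outputs, and the laboratory shifts and listings, from which a careful reader could reconstruct most of it. No test, power figure or sample size changes; SAP 8 plans no general inference on adverse event rates.

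The conclusion rests on SAP 3.2.1, 5.1.1, 8.1 and 11.3 as they stand, and on reading the SAP's severity words as the protocol's grades. It is worth correcting because safety is the primary objective and the missing figures are the ones the protocol uses to describe Cohort A.

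**What to change.** 1. Add DLTs and AESIs to SAP 3.2.1, with the definitions in protocol 7.1 and 8.2.8.
2. Add subject-count rows to the overall summary in 8.1, with zeros shown and preferably exact intervals: any DLT; any AESI; C-SSRS ideation type 3 to 5; high HADS or worsening depression; significant liver chemistry change. Footnote the DLT row as also being the Grade 3+ related AESI category, so that no duplicate row is needed. State how a serious event of that kind is counted, since 7.1 calls it an AESI while 8.2.8 limits AESIs to non-serious events.
3. For the HADS row, use the full protocol category, not a score above 12 alone, and reconcile the scoring direction between SAP 8.7 and protocol 8.1.6.2.
4. State that an event made severe only by the missing-grade rule in 6.7.2 is flagged when DLTs are counted.
5. Add one DLT/AESI listing to 11.3.

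If the sponsor prefers not to report these endpoints, declare and justify that in 5.1.1.

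The cost is a few rows, one listing and a little programming. The one uncertainty is the source: protocol 8.2.8 has AESIs reported on the SAE Report Form, and neither document says that the eCRF carries a DLT or AESI flag, so the status may have to be derived or taken from that form.
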